Background: Treatment in Intensive Care Units (ICU) is costly¹ and with an ageing population, by 2020 the demand for intensive care services is expected to increase by 50%.² One of the most common therapeutic interventions prescribed in intensive care is fluid resuscitation (using crystalloid or colloid solutions), with at least one third of patients managed in ICUs receiving this intervention on any given day.³ Several large-scale clinical trials⁴⁻⁹ and meta-analyses¹⁰⁻¹⁴ have provided evidence of how fluid resuscitation can impact on important patient outcomes such as need for dialysis and mortality.

Objective: The primary objective of this project is to describe international trends in the prescription of intravenous fluids for fluid resuscitation in adult intensive care patients and compare this to the same data collected in 2007 from SAFE-TRIPS.

Method: An international cross-sectional survey will be undertaken which audits fluid resuscitation practice in participating ICUs on a single day.

Sampling: Convenience sampling will be used, leveraging from the SAFE-TRIPS project.

Data collection: Total number of patients in the ICU on the study day; Availability and unit cost of resuscitation fluid; General patient demographic information; ICU admission diagnostic categories; APACHE II Score; Volume and name of crystalloid or colloid; Indication for resuscitation; Characteristics of fluid prescriber; Organ support (at time of fluid resuscitation episode); Physiology (at time of fluid resuscitation episode); and Total fluid volumes administered.

Outcome: The findings from this project will provide important insights into the process of translating evidence from clinical trials on fluid resuscitation into clinical practice.

2 General Information

2.1 Title

The Fluid Translation of Research into Practice Study (Fluid-TRIPS): An International Cross-Sectional Survey of Fluid Resuscitation Practice

2.3 International liaison committee

An international liaison committee will be set up to coordinate the communication and conduct of the study within each country or region (see section 11.3 and 12.2).

3.1 Current fluid resuscitation research

The SAFE study

In 1998, the Cochrane Injury Group Albumin Reviewers (CIGAR) published a systematic review and meta-analysis comparing the effects of albumin to a range of crystalloid solutions and concluded that the administration of albumin was associated with a significant increase in death (relative risk [RR] 1.68, 95% confidence intervals [CI] 1.26 to 2.23, p<0.01). Despite methodological limitations of this meta-analysis, this study caused substantial alarm, particularly in Australia where albumin was widely used.

As a result, our group at the George Institute, in collaboration with the Australian and New Zealand Intensive Care Society Clinical Trials Group (ANZICS-CTG), conducted the NHMRC funded Saline vs Albumin Fluid Evaluation (SAFE) study to examine the effect of resuscitation with 4% albumin to its carrier solution, saline, on death at 28 days in a population of adult ICU patients. The results published in the New England Journal of Medicine demonstrated no difference in death between albumin and saline (RR 0.99, 95%CI 0.91 to 1.09, p=0.87). This landmark study addressed a fundamental question about the safety of albumin for fluid resuscitation. The same study addressed a fundamental question about the safety of albumin for fluid resuscitation.

The SAFE-TRIPS study

As published evidence of fluid prescribing patterns was only available from surveys and questionnaires of clinician preferences conducted in a small number of ICUs in single countries, ¹⁷⁻¹⁹ the SAFE-Translation of Research into Practice Study (TRIPS) study was established³. The SAFE-TRIPS study was an international cross-sectional observational study conducted in 25 countries and 391 ICUs during 2007. The study aimed to assess which fluids were being used for resuscitation in critically ill patients. Fluid resuscitation was defined as the administration of either a bolus of crystalloid, colloid or blood product that was delivered within the time frame of an hour.

There were two key findings from the SAFE-TRIPS study: firstly, despite the absence of evidence of superiority and the associated increased costs, colloids were more frequently administered to resuscitate critically ill patients than crystalloids, with Hydroxyethyl starch (HES) the most commonly prescribed synthetic colloid. Secondly, the choice of fluid varied substantially and geographic location, rather than patient factors, appeared to be a strong determinant of practice variation.

[figure not shown]

Figure 1: Proportion of fluid resuscitation episodes in SAFE-TRIPS given as crystalloid, colloid and blood product according to country

The CHEST study

The findings from SAFE-TRIPS and the implications of Therapeutic Goods Administration (TGA) licensing of 6% HES 130 in Australia in 2006, provided the impetus to conduct a large-scale, high-quality RCT, modelled on the SAFE study. The Crystalloid vs. Hydroxyethyl Starch Trial (CHEST) compared resuscitation with the most commonly used colloid globally, 6% HES (130/0.4), to the most commonly used crystalloid globally, 0.9% saline, in ICU patients. This trial was conducted by our group at the George Institute and through the ANZICS-CTG. CHEST randomized 7000 intensive care patients who required fluid resuscitation, to either 6% HES (130/0.4) or 0.9% saline (the carrier fluid for 6% HES). This study demonstrated no difference on the primary outcome of 90 day mortality between the two groups (RR 1.06; 95% CI 0.96 to 1.18; P=0.26), nor any difference in mortality in predefined subgroups. However, the study did demonstrate that patients resuscitated with HES were significantly more likely to receive renal replacement therapy (RRT) compared to patients resuscitated with saline (RR 1.21; 95% CI 1.00 to 1.45; P=0.04). Importantly CHEST had a pre-published analysis plan, ²⁰ in which there was an *a priori* specification that the study design incorporated 90% power at an alpha of 0.5 to detect a relative increase in the risk of renal

failure by 1.5. There were also significant increases in the number of adverse events (predominantly cutaneous manifestations and increased need for blood product transfusion) in the HES group compared to the saline group.

The 6S Study

At the time CHEST was in the final stages of recruitment, the Scandinavian Starch for Severe Sepsis/Septic Shock study (6S) was published.⁴ This study assessed the effects of 6% HES (130/0.42) compared with a balanced crystalloid solution (Ringers acetate, which was the carrier solution for the HES preparation being evaluated in this study) on mortality and kidney failure in 798 patients with severe sepsis. The 6S investigators reported an increased risk of death at 90 days in those patients resuscitated with 6% HES (130/0.42) (RR 1.17; 95% CI 1.01 to 1.36; P=0.03). HES patients were also more likely to need renal replacement therapy (RR 1.35; 95% CI 1.01 to 1.80; P=0.04) compared to patients given Ringers acetate.

3.2 Rationale for Fluid-TRIPS

This proposed project – the Fluid Translation of Research Into Practice Study (Fluid-TRIPS) – is an international collaboration that will be coordinated by the George Institute for Global Health. Fluid-TRIPS builds on the infrastructure already established by SAFE-TRIPS³ and aims to provide key evidence to describe and understand international fluid prescribing habits in different regions of the world. This includes determining if patterns of fluid resuscitation within ICUs globally have been influenced by the publication of systematic review and meta-analyses^{10-14,21-23} and clinical trials, ^{4-6,8,9,24} since the SAFE-TRIPS study was conducted in 2007.

4 Aims and Objectives

The aim of this project is to describe international trends in the prescription of intravenous fluid resuscitation and to determine factors influencing choice.

4.1 Primary objectives

- 1. To describe the amount and type of resuscitation fluid currently administered to adult patients in intensive care units (ICU) in different countries
- 2. To compare the types of fluids used for resuscitation collected in this survey to data collected in the international survey conducted by our group in the 2007 Saline versus Albumin Fluid Evaluation Translating Research Into Practice Study.³

4.2 Secondary objectives

- 1. To describe and compare the costs of fluid choice between different geographical regions
- 2. To develop policy recommendations for practice guidelines

5 Study Design - Cross Sectional Survey

The study is based on the methodological design of SAFE-TRIPS. An international cross-sectional survey will be undertaken which audits fluid resuscitation practice in participating

adult ICUs on a single day, commencing at the beginning of the relevant chart day and including all patients in the ICU and admitted during the 24-hour study period. The cross-sectional survey will address both primary objectives.

5.1 Sampling

Convenience sampling will be used leveraging from the previous collaborators in SAFE-TRIPS (391 centres from 25 countries). Additionally, sampling will be sought through established ICU clinical trials networks.

5.2 Inclusion/exclusion criteria

Adult patients (16 years or older) present in the ICU at the start of the study day or admitted during the 24-hour study period will be included in the study sample. The study period will correspond to the local chart day in individual units.

5.3 Data source

Data will be extracted from patient clinical records and bedside notes during the study day.

5.4 Data collection

Data will be collected over a designated 24-hour study day. Screening will be conducted on all patients present in the ICU at the start of the study day or admitted during the 24-hour study period, with total patient numbers recorded for the study day. Data will be collected only on those patients receiving fluid resuscitation on the study day.

Fluid resuscitation will be defined as administration of any of the following:

- a bolus of crystalloid
- a crystalloid infusion of 5mL/kg/hour or greater for one or more hours
- · a colloid bolus
- any colloid by infusion

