7.2 Data analysis

Data analysis will be guided by a statistical analysis plan, which will be developed before the database is locked. Data analysis will be undertaken at the George Institute for Global Health by statisticians using SAS software. To address the primary objectives descriptive statistics will be used including univariate comparisons. Only sites participating in both SAFE TRIPS and FLUID TRIPS will be included in the comparison of fluid use over time. To address the secondary objective – a multivariate analysis will be completed adjusting for predictors of fluid choice. An example of the proposed analysis can be found in the SAFE TRIPS publication³.

8 Data Management

The data management and analysis will be undertaken by the George Institute for Global Health. The principal means of data collection and data processing will be via online data entry performed by the research coordinators at each site.

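### Primary objective 2 compares 2007 with the current survey although the protocol defines fluid resuscitation differently for each, so part of any change in fluid use may come from the definition

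*Protocol*

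**What the plan says.** Section 4.1 sets the second primary objective: "To compare the types of fluids used for resuscitation collected in this survey to data collected in the international survey" of 2007 (SAFE-TRIPS).

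For the 2007 survey, section 3.1 gives the case definition as "a bolus of crystalloid, colloid or blood product that was delivered within the time frame of an hour". The legend of Figure 1 shows that results were reported in the same three classes: "Proportion of fluid resuscitation episodes in SAFE-TRIPS given as crystalloid, colloid and blood product according to country".

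For the current survey, section 5.4 begins "Fluid resuscitation will be defined as administration of any of the following" and lists four items: a crystalloid bolus, "a crystalloid infusion of 5mL/kg/hour or greater for one or more hours", a colloid bolus, and "any colloid by infusion". Patient data are collected only for those who meet this definition.

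Section 5 states: "The study is based on the methodological design of SAFE-TRIPS". Section 7.2 assigns descriptive and univariate methods to the primary objectives and gives one comparability rule: "Only sites participating in both SAFE TRIPS and FLUID TRIPS will be included in the comparison of fluid use over time". It does not mention a common case definition.

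**The concern.** A comparison of two surveys over time needs the same case definition and the same denominator in both. Otherwise a change in what is counted is reported together with any change in practice. Restricting to common sites removes differences in site mix. It leaves untouched a difference in which events qualify.

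The definition matters twice here. It decides which episodes are classified, and because data are collected only on resuscitated patients, it also decides who enters the dataset. At stake is whether a shift between crystalloid and colloid since 2007 can be attributed to prescribing, which section 3.2 gives as a reason for the study.

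**Working it through.** **1. The two definitions side by side**

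| Element | 2007, per section 3.1 | Current, section 5.4 |
|---|---|---|
| Crystalloid bolus | yes, within an hour | yes, no time limit stated |
| Colloid bolus | yes, within an hour | yes, no time limit stated |
| Blood product | yes | not listed |
| Crystalloid infusion | not mentioned | yes, with a minimum rate and duration |
| Colloid infusion | not mentioned | yes, no minimum |

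**2. The plan's own yardstick**

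Section 7.1 claims 90% power for a 6-point change with 350 ICUs, 5 to 10 patients each, ICC 12% and baseline 50%. The protocol gives no alpha; two-sided 5% and two independent surveys are assumed here.

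- At 7.5 patients per ICU the design effect is 1 + 6.5 × 0.12 = 1.78.
- Effective n per survey = 350 × 7.5 / 1.78 = 1475.
- Power for 50% against 56% is 90.4%, so the stated figure reproduces (83.3% at 5 patients per ICU, 93.7% at 10).

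Six points is therefore a fair scale for judging an artefact. Nothing below depends on section 7.1 being wrong.

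**3. Dropping blood product, if the outcome is a share of episodes**

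Let c be a class's share of all 2007 episodes and b the blood share. With no change in practice, removing blood from one survey only shifts the share by c/(1 − b) − c. The protocol's text gives neither c nor b, so both are assumed.

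| b | Shift at c = 40% |
|---|---|
| 5% | +2.1 points |
| 10% | +4.4 points |
| 15% | +7.1 points |
| 20% | +10.0 points |

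The blood share that yields exactly 6 points is b = 1 − c/(c + 0.06):

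- c = 30%: 1 − 0.30/0.36 = 16.7%
- c = 40%: 1 − 0.40/0.46 = 13.0%
- c = 50%: 1 − 0.50/0.56 = 10.7%

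**4. Adding infusions, same outcome**

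Let x be newly counted infusion-only episodes of one class, as a fraction of the 2007-type episodes. The shift is (c + x)/(1 + x) − c. At c = 50%, x of 5, 10, 15 and 20% gives +2.4, +4.5, +6.5 and +8.3 points. Six points needs x = 0.06/(1 − 0.50 − 0.06) = 13.6%. These x values are assumed too. Crystalloid and colloid infusions push the shares in opposite directions and may partly cancel.

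**5. Other denominators**

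- *All ICU patients.* Dropping blood leaves crystalloid and colloid prevalence unchanged. The infusion items can only add patients: each 1% of ICU patients who received a class solely by a newly counted infusion adds one point to that class.
- *Resuscitated patients.* Only patients who received blood alone leave the denominator, so episode shares cannot simply be put into the formula in step 3.

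**6. Chance that an artefact is declared significant**

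At the size and under the assumptions of step 2, a pure artefact of 2, 3, 4 or 6 points would reach significance with probability 19%, 37%, 58% or 90%. The common-site subset may be smaller, so these are illustrations at the planned size.

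**The case against.** The 2007 definition is known here only from one sentence of background. The same group ran both surveys, section 5 says that the design follows the earlier one, and section 7.2 points to the 2007 publication as the model for analysis. The sentence may be an abbreviation. **This stands.** If it is, the fault lies in section 3.1, and the two sections still need reconciling.

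The blood calculation needs a share of episodes. Section 7.1 speaks of prevalence and counts patients, and the total number of ICU patients is recorded, so another denominator is possible. **This stands**, and it makes the figures in step 3 one scenario.

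The crystalloid infusion item may overlap the old rule: at an assumed 70 kg, its threshold for one hour is 350 mL, arguably close to a bolus given within an hour. **This stands in part.** Colloid infusion without any minimum has no counterpart in section 3.1.

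The SAP, due before database lock and not available here, could impose a common definition. **This stands in part.** Excluding 2007 blood episodes looks feasible at analysis. Section 5.4.2, however, lists episode times, fluid type and volume, and daily infusion totals, but no explicit bolus/infusion indicator or duration for each episode. Whether a bolus-only rule could be rebuilt is not shown.

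A reader might go further and infer that no observed change can be read as a change in practice, or that crystalloid use will appear to rise by a known amount. The documents support neither. They give no blood share and no counts by route, the infusion items may offset each other, and the denominator is not fixed.

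**Conclusion.** As written, sections 3.1 and 5.4 define fluid resuscitation differently for the two surveys, and the common-site rule in section 7.2 does not correct for this. Part of any change found under primary objective 2 may therefore reflect the definition. Neither its size nor its direction can be determined from the protocol.

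An artefact as large as the 6-point target is possible under modest inputs: a 2007 blood share of about 11% at a 50% baseline or 13% at 40%, provided that the outcome is a share of episodes with blood in the 2007 denominator. Both the shares and that outcome are assumptions. With all ICU patients as denominator the blood effect vanishes, and what remains is an upward shift in the current survey from the infusion items.

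The conclusion takes section 3.1 as an accurate account of the 2007 rule. If it is not, the infusion part becomes an error of description. The Figure 1 legend would still place blood product among the 2007 episodes.

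**What to change.** In this order:

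1. Check the definition actually used in the 2007 survey and reconcile sections 3.1 and 5.4. This comes first because limiting the current data to boluses of one hour or less would itself create a mismatch if 2007 did count infusions.
2. State in section 7.2 or the SAP that objective 2 uses only episodes meeting a definition common to both surveys, with the same named denominator, and with blood-product episodes excluded from the 2007 data.
3. If 2007 counted boluses only, make sure before the first data collection day that the eCRF separates bolus from infusion and records duration for each episode, so that the current data can be restricted. If 2007 also counted infusions, correct section 3.1 and do not restrict.
4. Keep the full section 5.4 definition for objective 1.

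The cost is a check of the 2007 documentation, a few sentences of text, possibly one extra eCRF field, and somewhat fewer current-survey episodes in the comparison over time.

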5.4.1 Site specific data collection

For ICUs participating in this study, a site questionnaire will also be administered to document the total number of patients in the ICU on the study day plus availability and cost of different fluid types.

5.4.2 Individual patient data

Patients who receive fluid resuscitation will have the following data collected:

Baseline data

- Sex
- Age
- ICU admission date
- Admission source and type
- Diagnosis
- Weight

- Diagnostic subcategories and details (trauma/sepsis/ARDS)
- GCS
- Cranial CT scan performed
- Abnormality on cranial CT
- Severity of disease score

Fluid Resuscitation Episode Data

- Time of resuscitation episodes
- Indications
- Prescriber characteristics
- SOFA score respiratory and cardiovascular only
- Renal replacement therapy
- Mechanical ventilation
- Non-invasive ventilation
- ECMO
- ICP monitor
- ICP value
- Heart rate
- MAP
- Systolic and diastolic ABP
- CVP
- PCWP
- Lab results (creatinine, bilirubin, base excess or deficit, lactate, serum albumin)
- Urine and fluid output previous complete hour
- Crystalloid type and volume
- Colloid type and volume
- Fluid resuscitation infusion totals for the study day
- Total daily fluid balance input and output volumes

6 Safety Monitoring

As this is a cross-sectional study using data collected as part of routine clinical practice, no safety monitoring will be undertaken.

7 Statistical Analysis Plan

7.1 Sample size and power

Due to the uncertain nature of observational research, no specific sample size has been calculated for this study. Based on the experience of SAFE TRIPS we anticipate recruiting a similar sample size (n>5000 patients; n>350 sites). A sample size of 280 ICUs and 2100 patients will allow us to estimate the overall prevalence of each fluid type very precisely with 95% confidence intervals that will be no wider than 6 percentage points. Furthermore,

we will be able to suitably estimate country specific prevalence rates with a precision of around 20 percentage points. Additionally, by recruiting between 5 and 10 patients from 350 ICUs, we will have 90% power to detect absolute changes in fluid prevalence over time of 6 percentage points.

All calculations assume a baseline prevalence of 50% which leads to the lowest precision (compared to lower prevalence assumptions); it is therefore likely that actual confidence intervals and detectable changes will be even smaller. These estimates also take into account the correlation of patients within ICUs. Based on the SAFE-TRIPS data, we have estimated that the Intraclass Coefficient (ICC) for fluid use is approximately 12%. Sample size calculations were performed using PASS 2008 and procedures appropriate for cluster-randomised studies.²⁵

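### Section 7.1 claims 90% power for 5 to 10 patients per ICU, but on a two-sided 5% test with independent periods power is about 83% at 5 and reaches 90% only from about 7.3

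*Protocol*

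**What the plan says.** Section 7.1 of the protocol gives three sets of numbers.

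- Expected recruitment: "we anticipate recruiting a similar sample size (n>5000 patients; n>350 sites").
- Precision: 280 ICUs and 2100 patients, for an overall 95% confidence interval at most 6 points wide.
- Power: the condition is "by recruiting between 5 and 10 patients from 350 ICUs", and the claim attached to it is a power of 90% for a 6-point change since 2007.

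The shared assumptions follow: "All calculations assume a baseline prevalence of 50% which leads to the lowest precision", and an intraclass correlation of about 12% estimated from the 2007 survey. The calculations are said to use cluster-randomised methods. Alpha and sidedness are not given for the power statement.

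Two other sections bear on it. Section 5.4 says "Data will be collected only on those patients receiving fluid resuscitation on the study day". Section 7.2 restricts the comparison over time to sites that took part in both surveys.

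**The concern.** A single power figure is attached to a twofold range of patients per ICU. With an intraclass correlation of 0.12, the effective sample size changes materially between 5 and 10 per ICU, so one figure cannot describe the whole range. If 90% belongs to the middle or top, it overstates power at the bottom.

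The three sets of counts also imply different numbers per ICU, and none is labelled as screened or analysed. The prevalence of a fluid type can be estimated only among resuscitated patients, so the label decides which power figure applies. Change since 2007 is the second primary objective (section 4.1), so this is the assurance a reader would rely on for that comparison.

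**Working it through.** **Inputs from section 7.1:** 350 ICUs; m = 5 to 10 patients per ICU; 0.50 against 0.56; intraclass correlation 0.12.

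**Assumed, because not stated:** two-sided 5% test; the same number of ICUs and patients per ICU in both periods; independent periods.

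**Formulas**

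- Design effect: DE = 1 + (m − 1) × 0.12
- Effective sample size per period: n_eff = 350 × m / DE
- Power = Φ{ [0.06 × √n_eff − 1.96 × √(2 × 0.53 × 0.47)] / √(0.50 × 0.50 + 0.56 × 0.44) } = Φ{ [0.06 × √n_eff − 1.3834] / 0.7046 }

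**Step 1: reproduce the stated 90%.** At the midpoint, m = 7.5, DE = 1 + 6.5 × 0.12 = 1.78 and n_eff = 2625 / 1.78 = 1474.7. Power = Φ(1.307) = 90.4%. The stated figure is recovered here, and 7.5 is also 2100/280.

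**Step 2: the rest of the quoted range.**

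| m | DE | n_eff | Power |
|---|---|---|---|
| 5 | 1.48 | 1182.4 | 83.3% |
| 6 | 1.60 | 1312.5 | 86.9% |
| 7 | 1.72 | 1424.4 | 89.5% |
| 7.5 | 1.78 | 1474.7 | 90.4% |
| 10 | 2.08 | 1682.7 | 93.7% |

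**Step 3: where 90% starts.** The unclustered requirement is 1453 per period. Setting 350m / (0.88 + 0.12m) = 1453 gives 175.64m = 1278.64, so m = 7.28.

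**Step 4: detectable change at the bottom of the range.** At m = 5, 90% power is reached for a change of 6.65 points, against the stated 6.

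**Step 5: the precision claim.** For 280 ICUs and 2100 patients, the width is 2 × 1.96 × √(0.25 × 1.78 / 2100) = 0.057, or 5.7 points. This is within the stated 6.

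**Step 6: the counts side by side.**

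- 5000/350 = 14.3 per ICU, at the stated bounds
- 2100/280 = 7.5 per ICU
- 5 to 10 per ICU over 350 ICUs = 1750 to 3500 patients

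If the 5000 are analysed patients, 14.3 lies above the quoted range and power is about 96%. If they are screened patients, the synopsis offers a conversion, "with at least one third of patients managed in ICUs receiving this intervention on any given day". Then 14.3/3 = 4.76 per ICU, DE = 1.451, n_eff = 1148 and power is 82.2%. This is a scenario only.

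**Step 7: sites in both surveys.** The 2007 survey had 391 centres (section 5.1), so 350 common sites would need 350/391, about 90%, to return. With an assumed 280 common sites and independent periods, n_eff is 1179.8 at m = 7.5 (power 83%) and 945.9 at m = 5 (power 74%).

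**The case against.** The best defence is that the range describes how individual ICUs vary around a mean of 7.5. That is the midpoint and the ratio behind the precision figure, and 90% is correct there. This reading is reasonable and probably explains where the figure came from. However, the sentence states no mean, and as written it offers 90% for any yield from 5 upward.

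Two technical readings would rescue the lower end. A one-sided 5% test gives 90.0% at 5 per ICU. Using the same ICUs in both surveys also helps if ICU effects persist. With an assumed between-period correlation of 0.5, the variance is 2 × 0.25 × (0.88/5 + 0.12 × 0.5)/350 = 0.000337 and power at 5 is about 90%. Both are possible, but section 7.1 mentions neither a one-sided test nor a between-period correlation, so the stated calculation cannot be credited with them. The paired-site argument also has a cost, because the same restriction may reduce the number of ICUs below 350.

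It is also fair to say that little turns on the figure operationally. Section 7.1 says no formal sample size was set, and the survey is descriptive with no decision rule. That limits the consequence but does not make the statement correct.

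A reader might go further and infer that the protocol's own numbers fix the yield at 4.8 per ICU and the power at 82%. They do not. The protocol never says the 5000 are all ICU patients, and 5000, 350 and one third are all lower bounds. More sites would lower the ratio and more patients would raise it, so 4.8 is neither a fixed value nor a floor. The share also comes from a survey whose definition of resuscitation included blood products (section 3.1), which section 5.4 does not list. Nor does the precision claim fail: a width above 6 points at 280 ICUs appears only if the stated 2100 patients are replaced by a smaller number.

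**Conclusion.** The point stands as an overstatement across part of a range. With 350 ICUs per period, intraclass correlation 0.12, 50% baseline, a two-sided 5% test and independent periods, power for 6 points is about 83% at 5 patients per ICU and 87% at 6. It reaches 90% from about 7.3 and 94% at 10. At the bottom of the range, the chance of missing a 6-point change is about 17%, not 10%. The first two conditions and the baseline are the protocol's; the test and the independence are assumed, and a one-sided test or strong between-period correlation would bring the figure at 5 up to about 90%.

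Separately, section 7.1 does not say whether its patient counts are screened or resuscitated, and its 350 ICUs may be optimistic for a comparison limited to common sites. The 82% figure is a scenario that depends on how the 5000 is read. The confidence interval claim is sound.

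**What to change.** Amend section 7.1 only.

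- Replace the single figure with power by mean number of analysed patients per ICU: about 83% at 5, 90% at about 7.5 and 94% at 10. Alternatively, say that 5 per ICU gives 90% power for about 6.7 points.
- State alpha, sidedness, the assumed mean number of resuscitated patients per ICU, and whether any between-period correlation is assumed.
- Label the 5000 as screened or analysed. If screened, show the one-third case (about 4.8 per ICU, about 82% power) as a scenario.
- Base the comparison over time on the number of sites expected in both surveys, with a lower case such as the assumed 280: about 83% at 7.5 and 74% at 5 if periods are independent, and more if ICU effects are correlated between periods.
- Leave the overall confidence interval claim unchanged.

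The cost is a few sentences of text. Data collection, eligibility and analysis do not change.

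### Section 7.1's 6-point interval width and 90% power match an equal-cluster calculation at 7.5 patients per ICU, but a one-day census without a quota will give unequal counts

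*Protocol*

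**What the plan says.** Protocol section 7.1 makes two main quantitative claims. The first concerns precision: for the overall share of each type of fluid, 280 ICUs with 2100 patients are said to give "95% confidence intervals that will be no wider than 6 percentage points". The second concerns change since 2007: "by recruiting between 5 and 10 patients from 350 ICUs, we will have 90% power" for an absolute change of 6 percentage points. (A looser country-level precision of about 20 points is also given and is not at issue here.)

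The section states its assumptions: "All calculations assume a baseline prevalence of 50% which leads to the lowest precision", an ICC of about 12% estimated from the 2007 survey, and cluster-randomised procedures in PASS 2008. On clustering it says "These estimates also take into account the correlation of patients within ICUs". Because 50% is the worst case, it considers it likely that actual intervals and detectable changes will be smaller still. It gives no CV of patients per ICU and mentions no allowance for unequal counts.

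Section 5.4 determines how many patients each ICU supplies: "Data will be collected only on those patients receiving fluid resuscitation on the study day". Sections 5.2 and 5.4 screen everyone present or admitted during the 24 hours, with no target or cap per ICU. Section 7.2 restricts the comparison over time to sites that took part in both surveys.

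**The concern.** The number of patients from an ICU is whatever number receives resuscitation fluid there on one day, so it depends on unit size and on chance. Section 7.1 itself expects a range. When cluster sizes vary, the variance of a pooled proportion is larger than the equal-size design effect implies, and never smaller. The precision claim is nevertheless worded as a firm upper bound and the power claim as a single unconditional value. The only remark on how the true figures may differ points towards better precision.

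These two figures support both primary objectives: current fluid use, and change since 2007. A small or null change would be judged against the claimed 90% power.

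**Working it through.** **Inputs from section 7.1:** 280 ICUs and 2100 patients (mean m = 2100/280 = 7.5); 350 ICUs with 5 to 10 patients each (midpoint 7.5, N = 2625); prevalence 50%; ICC 0.12; change of 6 points.

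**Assumptions, not in the protocol:** two-sided 5% test; the two surveys independent and of equal size; the CV of patients per ICU, shown as a range.

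**Formulas**
- Design effect: DE = 1 + ((1 + CV²)m - 1) x ICC, which is 1 + (m - 1) x ICC when CV = 0.
- Full 95% width = 3.92 x √(0.25 x DE/2100).
- Power = Φ(0.06/√(2 x 0.25 x DE/N) - 1.96).

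**Reproducing the plan's figures (equal counts, m = 7.5).** DE = 1 + 6.5 x 0.12 = 1.78. Width = 3.92 x √(0.25 x 1.78/2100) = 5.71 points. Power = Φ(0.06/√(0.5 x 1.78/2625) - 1.96) = Φ(1.30) = 90.3%. Both claims are matched.

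**Unequal counts at mean 7.5**

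| CV | DE | Width, points | Power |
|---|---|---|---|
| 0 | 1.78 | 5.71 | 90.3% |
| 0.33 (half the ICUs at 5, half at 10) | 1.88 | 5.86 | 88.7% |
| 0.37 (Poisson counts) | 1.90 | 5.90 | 88.4% |
| 0.5 | 2.00 | 6.06 | 86.7% |
| 0.6 | 2.10 | 6.20 | 85.0% |
| 0.8 | 2.36 | 6.56 | 80.8% |
| 1.0 | 2.68 | 7.00 | 75.7% |

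A power formula that uses 50% and 56% directly gives values up to about 0.2 points higher, for example 81.0% at CV 0.8.

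**Where the width passes 6 points.** DE must equal (0.06/3.92)² x 2100/0.25 = 1.968. Then (1 + CV²) x 7.5 = 0.968/0.12 + 1 = 9.07, so CV² = 0.209 and CV = 0.46.

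**The stated range of 5 to 10, equal counts, 350 ICUs**
- m = 5: DE = 1.48, N = 1750, power 83.1%.
- m = 7.5: DE = 1.78, N = 2625, power 90.3%.
- m = 10: DE = 2.08, N = 3500, power 93.6%.

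A two-sided 90% is therefore reached at the midpoint of the range but not at its lower end.

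**Same ICUs in both surveys.** With a between-survey correlation r of the ICU effects, and an ICU's count taken as the same in both surveys, DE in the power formula becomes 1 - ICC + (1 + CV²)m x ICC x (1 - r). The loss from unequal counts is fully offset when r = 1 - 1/(1 + CV²): r = 0.20 at CV 0.5 and 0.39 at CV 0.8. At r = 0.5 and CV 0.8, power is 92.8%.

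**The case against.** The arithmetic of section 7.1 is not wrong: both figures reproduce, and the sentence on within-ICU correlation is true as far as it goes. Several further points stand.

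- A reader might infer that the figures hold only if every ICU contributes the same number, so that any imbalance breaks both. The documents do not support this. The width stays within 6 points up to a CV of about 0.46, and imbalance confined to 5 to 10 at mean 7.5 costs under 2 points of power.
- A reader might also infer that the design lacks 90% power. That does not follow. The CV is not given, and section 7.2 compares the same ICUs, so a modest correlation over time could restore the power. But section 7.1 neither states nor claims such a correlation.
- The remark about smaller intervals is hedged and is correct about prevalence. At 30% prevalence and CV 0.5 the width is 5.55 points. The remark is incomplete because it covers only one of the factors.
- The protocol anticipates more than 5000 patients at more than 350 sites. If 5000 patients from 350 ICUs all received resuscitation fluid, the width would be 5.75 points even at CV 1.0. The bound, however, is stated for 280 ICUs and 2100 patients, and 5 to 10 patients from 350 ICUs is only 1750 to 3500.
- The test's sidedness is not stated. A one-sided 5% test gives about 90% at 5 patients per ICU, again with equal counts. At CV 0.5 (DE = 1.63) that falls to about 87%.
- Weighting ICUs by their information would lose less than the pooled proportion: about 6.1 points and 87% at CV 0.7.

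Finally, this is a convenience sample analysed mainly by descriptive statistics, and no recruitment decision depends on the result. That limits the consequence, but it does not justify a firm bound.

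**Conclusion.** The point holds in a limited form. Section 7.1's figures match an equal-size calculation at 7.5 patients per ICU, with a small margin on the width and almost none on the power, and no allowance is stated for counts that the census design will make unequal. For 280 ICUs and 2100 patients at 50% prevalence and ICC 0.12, the width exceeds 6 points above a CV of about 0.46 and lies between 6.1 and 6.6 points for CVs of 0.5 to 0.8. With independent surveys and a two-sided 5% test, power over those CVs is about 87% to 81%. Separately from any imbalance, it is about 83% at 5 patients per ICU, so a single 90% does not describe the stated range.

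Whether the figures are actually missed depends on two quantities that the protocol does not give: the CV of fluid-treated patients per ICU and the between-survey ICU correlation. The fault is a firm bound and an unconditional power stated without them. It is worth correcting because both primary objectives rely on these figures.

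**What to change.** In section 7.1:

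1. Recompute with DE = 1 + ((1 + CV²)m - 1) x ICC, taking the mean and CV of fluid-treated patients per ICU from the 2007 data that supplied the ICC, or showing a stated range.
2. Give the power across 5 to 10 patients per ICU, with the significance level and sidedness, instead of a single 90%. If credit is taken for measuring the same ICUs twice, state the between-survey correlation and its source. The replacement power should come from this recalculation and not be fixed beforehand.
3. Replace "95% confidence intervals that will be no wider than 6 percentage points" with a width of about 6 to 7 points, or with the recomputed value.
4. Keep the remark that actual figures will probably be better, but limit it to the effect of prevalence.

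The cost is one recalculation and a few changed words. No extra ICUs are needed. The downside is that the stated figures may become slightly less favourable.
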